3. STUDY PLAN AND PROCEDURES

3.1 Overall study design and flow chart

Patients with ER+ breast cancer who had 1 to 3 prior lines of endocrine therapy and up to one line of chemotherapy for MBC, excluding fulvestrant and tamoxifen, will be randomized in a 1:1 ratio to receive fulvestrant 500mg IM Q28 days with one extra dose on D15 of the first cycle (as a loading dose) plus palbociclib 125mg/day PO on a 21 days on/7 days off schedule or tamoxifen 20mg PO daily plus palbociclib 125mg/day PO on a 21 days on/7 days off schedule. Patient accrual will be a goal of 40 evaluable at up to 4 sites. At randomization, plasma will

be obtained for evaluation of ESR1-mt and a biopsy will be obtained when possible. During treatment, all patients will undergo ct-DNA ESR1 mutation evaluation every 28 days. Treatment will continue until disease progression or unacceptable toxicity. At the time of disease progression, a second biopsy will be obtained when possible and the last blood drawn for evaluation of ct-DNA ESR1-mt will occur. All tissue obtained will also undergo molecular analysis to determine the activity of mutant ESR1.

[figure not shown]

FIGURE 5. Study Schema

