6.3 Efficacy

Response and progression will be evaluated in this study using the international criteria proposed by the revised Response Evaluation Criteria in Solid Tumours (RECIST) Committee (version 1.1). Changes in only the largest diameter (unidimensional measurement) of the tumor lesions are used in the RECIST criteria. Patients will be evaluated for response after every 2 cycles of therapy. In the case of non-measurable disease (as defined in 6.3.2), progression of disease will be determined by the appearance of new metastatic lesions or clinical worsening secondary to the non-measurable metastatic site at the treating physician's discretion.

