6.3.4 Response Assessment

Target Lesions

When more than one measurable lesion is present at baseline all lesions up to a maximum of five lesions total (and a maximum of two lesions per organ) representative of all involved organs should be identified as **target lesions** and will be recorded and measured at baseline (this means in instances where patients have only one or two organ sites involved a maximum of two and four lesions respectively will be recorded).

Evaluation of Target Lesions

- Complete Response (CR): Disappearance of all target lesions. Any pathological lymph nodes (whether target or non-target) must have reduction in short axis to <10 mm.
- Partial Response (PR): At least a 30% decrease in the sum of diameters of target lesions, taking as reference the baseline sum diameters.
- Progressive Disease (PD): At least a 20% increase in the sum of diameters of target lesions, taking as reference the smallest sum on study (this includes the baseline sum if that is the smallest on study). In addition to the relative increase of 20%, the sum must also demonstrate an absolute increase of at least 5 mm. (Note: the appearance of one or more new lesions is also considered progression).
- Stable Disease (SD): Neither sufficient shrinkage to qualify for PR nor sufficient

increase to qualify for PD, taking as reference the smallest sum of diameters while on study.

Non-target lesions

All other lesions (or sites of disease) including pathological lymph nodes should be identified as **non-target lesions** and should also be recorded at baseline. Measurements are not required and these lesions should be followed as ‘present’, ‘absent’, or in rare cases ‘unequivocal progression’. In exceptional circumstances, unequivocal progression in non-target lesions may be accepted as disease progression. In addition, it is possible to record multiple non-target lesions involving the same organ as a single item on the case record form (e.g. ‘multiple enlarged pelvic lymph nodes’ or ‘multiple liver metastases’).

When the patient only has non-measurable disease, the increase in overall disease burden should be comparable in magnitude to the increase that would be required to declare PD for measurable disease: i.e., an increase in tumor burden from “trace” to “large”, an increase in nodal disease from “localized” to “widespread”, or an increase sufficient to require a change in therapy.

Evaluation of Non-Target Lesions

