9. STUDY MANAGEMENT

9.1 TABLE 4. Study timetable and end of study

Procedure	Screening ^a	Visit 1	Every 4 weeks	Every 8 weeks	Off Treatment	Follow Up
INFORMED CONSENT	X					
CLINICAL ASSESSMENTS						
Physical Exam	X	X	X ^b		X	X ^c
Medical History	X	X				X ^c
Vital Signs, Height, Weight	X	X ^d	X		X	(X)
ECOG Performance Status	X	X	X		X	
LABORATORY TESTS:						
Hematology (CBC with diff, platelets)	X	X ^e	X ^f		(X)	
Chemistries and liver function tests ^g	X	X ^e	X ^f		(X)	
PT, INR, PTT ^q	X					
Estradiol ^h	X					
Pregnancy Test ⁱ	X			X		
IMAGING:						
CT Chest/Abd/Pelvis ^j	X ^j			X	(X)	(X)
Brain MRI	X ^k				(X)	(X)
TREATMENT:						
Tamoxifen		X ^L				
Fulvestrant		X	X ^L			
Palbociclib		X ^P				

OTHER ASSESSMENTS:						
Concomitant Medication Review	X	X	X		X	
Symptom/Toxicity Assessment	X	X	X		X ^m	
Follow-up/Survival					X ⁿ	X ^c
CORRELATIVE STUDIES						
Blood collection for ESR1-mt analyzed by ct-DNA	X		X		X	
Archived tissue sample (from breast primary)	X					
Optional Solid Tumor Biopsy	X ^o				X ^o	

- a) Screening assessments are required within 28 days of initiation of treatment unless otherwise noted.
- b) Required ≤ 1 day prior to each specified treatment (exceptions may be made to extend this window, with approval by the Protocol Chair/designee).
- c) To continue until patient death
- d) Height at baseline only
- e) Required ≤ 14 days prior to first day of treatment; baseline labs may be used if within window.
- f) Required ≤ 1 day prior to each specified treatment (exceptions may be made to extend this window, with approval by the Protocol Chair/designee).
- g) Chemistries to include measurement of sodium, potassium, chloride, CO₂, BUN, creatinine, glucose, total bilirubin, calcium, total protein, albumin, AST, ALT, and alkaline phosphatase.
- h) Estradiol if required to determine post-menopausal status can be performed any time prior to Visit 1 treatment
- i) Serum Pregnancy test is required for women of childbearing potential only. Required ≤ 7 days prior to first treatment (i.e., day 1) unless otherwise noted. All outcomes of pregnancy should be reported to the PI and AstraZeneca.
- j) PET/CT is allowed and the choice between using a CT or PET with CT will belong to the treating physician. If a PET is chosen, the CT is mandatory and must be of diagnostic quality.
- k) Only if known CNS metastasis

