11. EVALUATION AND CALCULATION OF VARIABLES

11.1 Calculation or derivation of efficacy variable(s)

The primary objectives of the study are descriptive assessments of ESR1 mutation detection in plasma. One of the secondary endpoints of the study is PFS. PFS is defined as the duration of time from time of randomization to time of progression or death, whichever occurs first. PFS for a subject without an event will be censored on the date of last tumor assessment. If an interval of 6 months passes without a tumor assessment, PFS will be censored at the time of the earlier tumor assessment, even if an event (progressive disease or death) is later observed. If a patient has not had an event, PFS will be censored at the date of the last adequate tumor evaluation. PFS will also be censored at the date of tumor evaluation when the next tumor evaluation (or death) is >6 months after the previous evaluation without an event. PFS will be assessed via local radiology assessment according to RECIST 1.1.

Although central review may occur as part of site calibration or an audit, the local assessment will be considered as the basis for the primary efficacy analysis. In the absence of measurable disease at baseline, the following criteria (per RECIST 1.1) will be used to assess disease progression among the patients with nonmeasurable lytic or mixed (lytic + blastic) bone lesions: 1) The appearance of one or more new lesions or 2) Unequivocal progression of existing non-measurable lesions.

Additional secondary endpoints include response rate, clinical benefit rate, (defined as CR+PR+ SD at any tumor assessment), clinical benefit rate at 6 months (CBR6), in the entire cohort, and the ESR1-mut cohorts. Response rate will be reported from best overall response according to RECIST 1.1 and as described in section 6.3. The response rate will then be compared amongst the tamoxifen plus palbociclib and fulvestrant plus palbociclib arms in the entire cohort and in the subgroup of ESR1-mt patients.

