12.1 Statistical analysis plan

The primary analysis will be conducted at least 6 months after the last patient is enrolled. Cox proportional hazards regression will be used to estimate hazard ratios comparing PFS for tamoxifen plus palbociclib and fulvestrant plus palbociclib. Fulvestrant will be considered promising for the unselected population if the fitted hazard ratio is < 0.8 , and for the ESR1-mut subpopulation if the hazard ratio is < 0.65 .

Response rate will be compared between treatment arms using the mid-P correction to Fisher's exact test for univariate comparisons, and logistic regression for exploratory multivariable models. Cox proportional hazards regression will be used for analyses with overall survival as the endpoint.

Adverse events will be reported for all patients in the safety cohort defined above, summarized by treatment group. Adverse events and serious adverse events will be tabulated in order of prevalence, with the highest grade reported by each patient.

Concordance of ESR1 status in plasma and biopsy samples will be assessed primarily by agreement regarding presence/absence of mutations for tissue and blood samples collected no more than 30 days apart and without intervening therapy. Kappa statistics adjusted for clustering (both pre-therapy and post-therapy time points for some subjects) will describe basic agreement. Additionally, between-subject and within-subject variation in mutant allele frequency will be compared using linear mixed models and the concordance correlation coefficient. This approach (complementary **analysis of categorical and continuous versions of**

ESR1 mutation status) may also be applied to assessment of within-patient longitudinal change. The primary analysis for these correlative studies will examine presence and allele frequency of any ESR1 mutation. Secondary analyses will examine and compare tissue-blood concordance and longitudinal change in liquid biopsy measures for specific ESR1 mutations. Level and change in circulating levels of ESR1-mt will be assessed as predictors of PFS using Cox proportional hazards regression with time-varying covariates. All hypothesis tests will be two-sided.

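### Does the time-varying Cox model for ESR1-mt and PFS need a lag and a written definition of change?

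*Combined protocol and SAP*

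**What the plan says.** The model is stated once, in section 12.1: "Level and change in circulating levels of ESR1-mt will be assessed as predictors of PFS using Cox proportional hazards regression with time-varying covariates". The same paragraph names presence and allele frequency of any ESR1 mutation as the measures for the correlative work, and says that paired categorical and continuous analyses "may also be applied to assessment of within-patient longitudinal change". Hypothesis 3 in section 1.2 and primary objective 1 in section 2.1 also speak of allele frequency.

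On timing, section 3.1 says "all patients will undergo ct-DNA ESR1 mutation evaluation every 28 days" and that at progression "a second biopsy will be obtained when possible and the last blood drawn for evaluation of ct-DNA ESR1-mt will occur". The row "Blood collection for ESR1-mt analyzed by ct-DNA" in Table 4 (section 9.1) marks screening, every 4 weeks and off treatment. Section 6.3 sets the scans: "Patients will be evaluated for response after every 2 cycles of therapy". The endpoint is in section 11.1: "PFS is defined as the duration of time from time of randomization to time of progression or death, whichever occurs first".

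The aims served are hypothesis 3 (change in allele frequency is associated with PFS) and secondary objective 2 in section 2.2 (correlation of longitudinal change with clinical outcome).

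**The concern.** Section 12.1 does not say whether change is measured from baseline or from the previous draw, on what scale, how undetected samples enter, or which draw supplies the covariate at an event. It mentions no lag.

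The schedule makes this look serious. With 4-weekly blood and 8-weekly scans, a draw can be taken after the tumour has progressed but before a scan records it. Progression of target lesions also needs a 20% rise, and "the sum must also demonstrate an absolute increase of at least 5 mm" (section 6.3.4), so smaller growth can pass a scan. A marker that only accompanies progression would then seem to precede the recorded event. Section 12.1 calls the marker a predictor, and section 12.2 says the results will shape later studies. A concurrent rise could be carried forward as an early-warning signal, and the result might depend on which definition of change the analyst chose.

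**Working it through.** The plan gives no power, event count or effect size for this analysis, so there is no stated figure to reproduce.

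**Inputs from the document.** Draws every 4 weeks and scans every 8 (sections 3.1, 6.3 and 9.1); n = 40 (section 12.2); 25% expected positive in plasma (section 6.3.5), so 40 × 0.25 = 10 patients.

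**Inputs assumed.** Exponential time to true progression, and the size and timing of the marker rise. True progression here means the unobserved onset; it is not the protocol's endpoint. Delays of 0, 28 and 56 days before a scan can detect it are also assumed.

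**1. Schedule.** Let λ = ln 2 / median in weeks (4.345 weeks per month). If progression is always seen at the next scan, the share with the mid-interval draw after true progression is f = 1/(1 + e^(−4λ)).
- Median 4 months (17.4 weeks): e^(−4λ) = 0.853, f = 1/1.853 = 0.54.
- Median 12 months (52.1 weeks): e^(−4λ) = 0.948, f = 1/1.948 = 0.51.

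If detection is 28 days late, every scan-detected progression has that draw after true progression. The draw 8 weeks before the scan is then also affected in e^(−4λ) × f of cases: 0.853 × 0.540 = 0.46 and 0.948 × 0.513 = 0.49.

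**2. Effect on the hazard ratio.** Simulated cohorts of 200,000 patients: binary detection, 25% or 50% showing the mutation, 5% unrelated detection per draw, median PFS 16, 26 or 48 weeks, no detection delay.

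| Draw used | No lead | True 16-week lead |
|---|---|---|
| Day of recorded progression | 3.0–9.7 | 1.6–4.7 |
| Previous draw (4 weeks) | 2.3–5.0 | 1.8–5.4 |
| 8-week lag | 1.00–1.01 | 2.0–6.4 |
| 12-week lag | 0.99–1.02 | 2.4–7.7 |

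An unlagged association therefore does not establish lead. It remains a valid association with recorded PFS.

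**3. At the trial's size.** Simulated trials with n = 40, 10 positive, all positives rising, median 8 months, log-scale noise SD 0.4. Percentage with p < 0.05 for change from baseline, abrupt five-fold rise:

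| Scenario | Earlier draws, no lag | 4-week lag | 8-week lag | 12-week lag |
|---|---|---|---|---|
| No lead, no delay | 67 | 62 | 6 | 7 |
| No lead, 28 days late | 98 | 96 | 52 | 7 |
| 4-week lead, no delay | 96 | 94 | 51 | 7 |

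Rows 2 and 3 are practically the same. A lag dates the rise against recorded progression only; it cannot separate a true lead from late detection.

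**4. Definition of change.** For a five-fold rise 12 weeks before true progression, the unlagged model finds it in 54% of trials when change is from baseline and 6% when change is from the previous draw. With no lead and no delay the two definitions nearly agree. For four rises (abrupt five-fold, abrupt two-fold, five-fold over 8 weeks, doubling every 8 weeks) the figures are 67, 32, 16 and 9% from baseline against 66, 28, 14 and 7% from the previous draw.

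**5. What a stricter plan would buy.** Take a rule that calls the marker predictive only if the association holds at both 8 and 12 weeks. For a five-fold rise:
- Power is 2.5% for a 4-week lead and 74% for a 12-week lead.
- With no lead it passes 0.7%, 2.6% and 57% of trials at delays of 0, 28 and 56 days.

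A week-8 landmark has 16% power (4-week lead) and 19% (12-week lead). With no lead it is positive in 6%, 16% and 32% at the three delays. It also drops patients who progress by the first scan: 1 − e^(−8λ) = 1 − 0.853² = 27% at a 4-month median and 1 − 0.948² = 10% at 12 months.

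**The case for a change.** The strongest case for amending is that the gap matters even if only association is wanted. Under one plausible pattern two analysts following section 12.1 could find the signal in 54% or in 6% of trials. Section 1.1 also speaks of ESR1 mutations as prognostic and predictive, and adding wording would cost little and need no new samples.

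The silence on reference draw, transformation and undetected samples is real, and so is the limit on interpretation. The rest carries less weight:

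- Allele frequency is already named as the measure, and the screening sample is the only pre-treatment draw in Table 4. Baseline is therefore the natural reference for change on therapy.
- Standard start-stop coding uses values known before the event, so a draw dated on the event day does not explain that event. Step 2 shows that the previous draw alone still gives 2.3 to 5.0, so the coding does not remove the limit on interpretation.
- No lag is stated, but none is excluded, and *predictor* is the usual word for a regression covariate. The remark in section 1.1 is background.
- The endpoint is RECIST progression or death. Growth below the threshold is not progression under the plan, so counting it as late detection substitutes a different endpoint.
- The sizes depend on the assumed rise. If only half of the positives rise, the 67% for an abrupt five-fold rise drops to 25%. Section 6.3.5 expects levels to fall on fulvestrant, which the simulations leave out.

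**Conclusion.** No change follows. The model as written answers the questions the plan asks, association and correlation with recorded PFS, and the treatment comparison does not depend on it. What is missing is detail that a competent analyst fills sensibly: change from the baseline draw, a stated scale and rule for undetected samples, and draws dated before the event. The result should be read as association with recorded PFS. It would not show that a rise comes before progression, and the plan does not say that it would.

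A prescribed set of lags or a landmark is a debatable trade-off with no clear gain. It gives up most short-lead signals (2.5% power at 4 weeks), does not protect against long detection delays (57% at 56 days), and would put a pass/fail rule on an exploratory analysis with about 10 positive patients and, under the assumptions used, 6 to 7 events among them. The schedule, sample size and 25% prevalence come from the document. Rise pattern, noise, delay and PFS distribution are assumptions, so the simulated figures show direction and do not forecast the trial's results.

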12.2 Sample size justification

The study sample size is restricted by external constraints: a planned study with a PFS endpoint powered to direct future therapy choices failed to accrue, in part because of the ever-shifting treatment landscape as described above. A study with n=40, 20 each receiving fulvestrant plus palbociclib or tamoxifen plus palbociclib, will allow sufficient exploration of a variety of study aims, in order to prioritize and inform the aims of future studies. If a sufficient number of accrued patients have ESR1-mt disease, it may be feasible to evaluate the association between mutational burden and response to continued endocrine+palbociclib therapy. Alternatively, there may be a strong signal for evolution of mutational frequency as different for patients receiving fulvestrant+palbociclib versus tamoxifen+palbociclib. Similarly, there may be a signal suggesting that continued endocrine+palbociclib therapy is associated with clinical benefit only in patients with ESR1-mt tumors who receive fulvestrant+palbociclib

APPENDIX A

List of medications that interact with CYP2D6, CYP3A4/5, CYP2C8/9 and CYP2D6 and should be avoided:

alfentanil
alprazolam
alprenolol
amitriptyline
amlodipine
amodiaquine2
amphetamine
aprepitant
aripiprazole
astemizole

atomoxetine
atorvastatin
boceprevir
bufuralol1
buspirone
cafergot
carbamazepine
carvedilol
celecoxib
cerivastatin

cerivastatin
chlorpheniramine
chlorpromazine
cilostazol
cisapride
clarithromycin
clomipramine
clonidine
cyclosporine
dapsone

desipramine	paclitaxel
dexamethasone	paroxetine
dexfenfluramine	perhexiline
dextromethorphan1	perphenazine
dextromethorphan2	phenacetin
diclofenac1	phenformin
diltiazem	pimozide
docetaxel	piroxicam
domperidone	progesterone
donepezil	promethazine
duloxetine	propafenone
encainide	propranolol
eplerenone	quetiapine
estradiol	quinine
felodipine	repaglinide
fentanyl	risperidone
finasteride	ritonavir
flecainide	romidepsin
fluoxetine	rosiglitazone
fluvastatin	salmeterol
fluvoxamine	saquinavir
gleevec	sildenafil
glibenclamide	simvastatin
glimepiride	sirolimus
glipizide	S-metoprolol
glyburide	sorafenib
haloperidol	sparteine
hydrocortisone	sunitinib
ibuprofen	suprofen
imipramine	tacrolimus (FK506)
indinavir	telaprevir
irbesartan	telithromycin
irinotecan	terfenadine
lercanidipine	thioridazine
lidocaine	timolol
lornoxicam	tolbutamide
losartan	tolbutamide1
lovastatin	torisel
meloxicam	torse mide
methadone	tramadol
methoxyamphetamine	trazodone
metoclopramide	triazolam2
mexiletine	valproic acid
midazolam1	vemurafenib
minaprine	venlafaxine
nateglinide	verapamil
nebivolol	vincristine
nelfinavir	zakirlukast
nevirapine	zaleplon
nifedipine2	ziprasidone
nisoldipine	zolpidem
nitrendipine	zuclopenthixol
nortriptyline	
ondansetron	
oxycodone
